6.3.1 Non serious AR/AEs

All such toxicities, whether expected or not, should be recorded in the Adverse Event eCRF which is completed by site staff and signed by the site PI.

6.3.2 Serious AR/AEs

For the purposes of this clinical study, all SARs will be considered SUSARs.

All SAEs must be reported to the Sponsor immediately (within 24 hours of the site becoming aware of the event). At a minimum, the following information should be included: nature of event, date of onset, severity, corrective therapies given, outcome and causality (*i.e.* unrelated, unlikely, possible, probably and definitely). The responsible investigator should sign the causality of the event. Additional information should be sent to the Sponsor within 5 days, if the reaction has not resolved by the time of reporting.

6.3.3 SAEs

It is the investigator's responsibility to report all SAEs to the Trial Manager and CI immediately (within 24 hours of the site team becoming aware of it). It is the Trial Managers responsibility to then report this to the Sponsor immediately.

If an adverse event is classed as serious, the AE form in the eCRF is completed and the SAE box ticked. At the point an AE is classed as serious, an email automatically goes to the Project Team to inform them of this. Additionally, a detailed SAE paper form then required completing by the site staff and site PI. This form is reviewed by the PI, who adds their comments and diagnosis before signing it off. This paper form must be emailed to the Trial Manager and CI within 24 hours of the site team being made aware of the SAE, who subsequently inform the Sponsor.

Additional information should be sent to the Trial Manager and CI, and additionally forwarded onto the Sponsor within 5 days, if the reaction has not resolved by the time of initial reporting.

Disease progression and hospitalisations for elective treatment of a pre-existing condition do not need reporting as SAEs.

6.3.4 SUSARs

It is the investigator's responsibility to report all SUSARs to the Trial Manager and the CI or CI delegate:

• The site staff and site PI must complete the SAE form (in addition to the AE eCRF with SAE box ticked), and send it immediately (within 24 hours and via email) signed and dated, together with the relevant treatment forms and anonymised copies of all relevant investigations.

[figure not shown]
OR

• Contact the Trial Manager by phone and then send the completed SAE eCRF within 24 hours as above

It is the Trial Managers responsibility to:

- Inform the Sponsor of all SUSARs
- Ensure that the CI/CI delegate has reviewed and signed off all SUSARs prior to reporting to MHRA and REC
- Notify the MHRA and REC of all SUSARs occurring during the study, according to the following timelines; fatal and life-threatening, within 7 days of notification, and non-life threatening, within 15 days.
- Inform all investigators of all SUSARs occurring throughout the study.

Safety Reporting Overview

7. ASSESSMENT AND FOLLOW-UP

Study Assessments and relevant timings are detailed below. In the event that protocol specified procedures and/or timings cannot be adhered to, due to any prevailing COVID19 restrictions, these will **not** be considered protocol deviations but will be documented in a specific COVID19 section of the eCRF.

7.1 Safety Assessments (Dose Escalation Stage)

7.1.1 Laboratory safety analysis

Haematology (FBC), biochemistry and urinalysis will be performed WEEKLY in Cycle 1 of treatment EVERY OTHER WEEK during Cycle 2 and then 4-WEEKLY thereafter from Cycle 3 onwards. Testing can be performed within a 72 hour time frame before the next scheduled Day 1 of dosing),

For myeloma patients the following tests must be performed no more than 72 hours prior to day 1 of dosing:

- Serum Protein Electrophoresis (SPEP)
- Paraprotein Quantification
- Serum Immunofixation
- Serum Immunoglobulin Levels
- Serum Free light chains
- 24h urine Bence Jones protein

Coagulation (aPTT, PT) will be assessed 4-WEEKLY.

Serum pregnancy test (where appropriate) at beginning of each cycle of DTP3 and then monthly for six months after cessation of DTP3 therapy.

7.1.2 Blood Pressure and Pulse Rate and 12 Lead ECG

These will be performed according to the following schedule (+/- 5 minutes):

Cycle 1: Week 1 and Week 2	Day 1, Day 3, and Day 5 (15 min before and 30 min, 60 min, and 120 min after the end of each DTP3 infusion)
Cycle 1: Week 3 and Week 4	15 min before and 30 min after the end of each DTP3 infusion
Cycle 2 onwards	15 min before and 30 min after the end of each DTP3 infusion

7.1.3 Adverse Events and Concomitant Medications

Prior to each DTP3 infusion (with follow up of ongoing AEs as necessary after completion of DTP3 therapy).

7.2 Safety Assessments (Expansion Stage)

7.2.1 Laboratory safety analysis

Haematology, biochemistry and urinalysis will be performed WEEKLY in Cycle 1 of treatment (within a 72 hour time frame, up to 3 days prior to infusion), EVERY OTHER WEEK during Cycle 2, and then 4-WEEKLY thereafter from Cycle 3 onwards. Testing can be performed within a 72-hour time frame before the next scheduled Day 1 of dosing),

Coagulation (aPTT, PT) will be assessed 4-WEEKLY.

Serum pregnancy test (where appropriate) at beginning of each cycle of DTP3 and then monthly for six months after cessation of DTP3 therapy.

7.2.2 Blood Pressure and Pulse Rate and 12 Lead ECG

These will be performed 15 min (+/- 5 min) before and 30 min (+/- 5 min) after the end of each DTP3 infusion for Doses 1, 2 and 3 (Week 1) and then before the first dose of DTP3 at the beginning of Week 2 onwards [*i.e* before Dose 4, Dose 7, Dose 10 *etc*]

7.2.3 Adverse Events and Concomitant Medications:

Prior to each DTP3 infusion (with follow up of ongoing AEs as necessary after completion of DTP3 therapy).

7.3 Pharmacokinetics

Blood samples (4 mL) will be taken for the analysis of DTP3 levels during Cycle 1 of DTP3 dosing. Where possible, patients will be admitted overnight on Day 1 of Cycle 1 to permit prolonged blood sampling for PK analysis.

Blood samples will be collected according to the following schedule:

Cycle 1 Day 1:

Pre-infusion, 5 min, 15 min, 30 min, 1 hr, 2 hr, 4 hr, 8 hr, 12 hr, 16 hr and 24 hr post- infusion

It is anticipated that full overnight PK sampling will be performed in nearly all patients, although this is at the discretion of each investigator. For exceptional patients who cannot be hospitalised (for logistical reasons), the following outpatient schedule will be adopted:

Pre-infusion, at 5 min, 15 min, 30 min, 1 hr, 2 hr and 4 hr post- infusion

Cycle 1 Day 3:

Pre-infusion

Cycle1 Day 5:

Pre-infusion, and at 0.5 hr, 1 hr, 2hr and 4 hr post- infusion

Blood samples will be collected by direct venepuncture or from an indwelling cannula into a labelled tube containing the appropriate anticoagulant, Further details will be provided in the separate DTP3 pharmacokinetic blood sampling manual.

For PK samples taken during the first hour of sampling, these samples need to be taken as precisely as possible at the specified time points, ideally within a window of +/- 2 minutes. For samples taken after the first hour and up to 8 hours, there can be a small window of +/- 5 minutes, for samples taken at 12 hours and later a window of 30 minutes is allowed. The exact time of bleeding will anyway be always registered on the log for all patients.

.

The blood samples will be processed, split, stored and shipped according to the sample processing instruction document mentioned above.

7.4 Pharmacodynamics

Mandatory samples (unless technically not possible) for pharmacodynamic (PD) assessment will be taken as follows:

- At screening (within 28 days prior to DTP3 treatment)
- **24 hours** (range 18-36 hr) after the **fourth dose** of DTP3 treatment (Cycle 1, Week 2, Day 2)

Tissue will be collected as follows on each occasion for PD, genetic and biomarker assessment and sent in their entirety to the Hammersmith site ([name] lab):

- MM: 50 mL of blood and 10 mL of bone marrow aspirate
- DLBCL: 50mL of blood and a tumour biopsy (18G core), if accessible.

7.5 *Efficacy* Assessments

7.5.1 MM

Routine efficacy assessments will be performed every 4 WEEKS (see Trial Assessment Schedule, Appendix C) unless clinically indicated at an earlier time point. The following assessments will be performed on a 4-weekly basis:

- Serum protein electrophoresis and paraprotein quantification
- Serum free light chain
- 24h urine collection electrophoresis (only in patients with detectable urinary M protein at screening)
- Biochemistry panel
- Full Blood Count

The necessity for bone marrow aspirate and biopsy and/or radiological imaging will be determined by the patient's individual clinical course and will only be undertaken when judged appropriate by the investigator for determination of response or progression, as follows:

If a complete (or stringent complete) response is suspected:

Two independent measurements (according to normal institutional practice) are required to confirm:

- negative immunofixation: serum
- negative immunofixation: urine

If these two independent measurements are consistent with the definition of a complete response, then a bone marrow aspirate and biopsy should be performed

If progression is suspected:

This can be determined by measurement of any relevant disease parameter, including radiological imaging and/or bone marrow plasma cell percentage, but should be confirmed by two independent measurements, according to normal institutional practice.

7.5.2 DLBCL

FDG-PET/CT imaging will be performed every 8 WEEKS after the first dose of DTP3, unless clinically indicated at an earlier time point (*e.g.* if there is clinical suspicion of disease progression).

A bone marrow aspirate and biopsy is required for confirmation of radiological complete response in patients who had a positive bone marrow aspirate/biopsy at screening.

Response assessment at each FDG-PET/CT timepoint will be made according to the Lugano 2014 criteria (Appendix B).

7.6 End of Treatment Visit

Following cessation of DTP3 therapy, for any reason other than death, all patients will have an End of Treatment Visit performed within a minimum of 3 days and a maximum of 28 days of the last dose of DTP3. The End of Study Visit must take place BEFORE the next treatment regime starts.

If the EOS visit takes place before day 28 post-DTP3 treatment, an EOS safety call will additionally take place. This safety call should occur on or just after day 28 after completing DTP3 treatment, to capture any final AEs covering the period of 28 days following the final DTP3 dose. Alternatively, this call can take place immediately before the patient is to commence a new treatment regime should a new treatment be planned to begin within 28 days of completing DTP3.

The following assessments should be performed:

- 12-Lead ECG
- Vital Signs (Blood Pressure, Pulse Rate)
- Symptom directed physical examination, including ECOG performance status
- Adverse Events and Concomitant Medications
- Pregnancy Test (where appropriate)
- Discussion with the patient of any clinically relevant incidental findings detected during the course of the study (if not already discussed with the patient at an earlier timepoint).

Should a participant be starting a new treatment drug after DTP3 treatment, there is a strict minimum washout safety period after the final dose of DTP3 of 5 days. This wash-out period has been selected based on at least 5-times the elimination half-life (t1/2) of DTP3. A final safety follow-up period of 5 days after the last dose of DTP3 is therefore required if the patient needs to start a new treatment before the scheduled 28-day safety follow-up. Starting a new treatment within this 5-day washout period would be classified as a serious protocol violation and subject the patient to potential drug interactions, this must be avoided. Therefore, any new drug treatments should start after the minimum 5 days washout period from DTP3, with the final AE check conducted immediately prior to commencing the new treatment if this is within 28-days of completing DTP3.

7.7 Follow Up

All patients who do not have disease progression at the time of ceasing DTP3 treatment will be followed, through routinely scheduled clinic visits for disease progression [according to the schedule in 7.5 above] and survival for a period of six months after the last patient has been recruited into the study.

Patients with disease progression at the time of ceasing DTP3 treatment will be followed up through routinely scheduled clinic visits for subsequent anti-cancer therapies and survival.

Patients' disease progression and survival status should be followed up a minimum of every 6 months, but ideally every 3-4 months through their attendance at routine clinic appointments.

Patients not being actively followed in the clinic will be contacted (or *via* a family member as appropriate) at approximately 2-3 monthly intervals to assess survival status.

Every effort should be made to follow-up patients who have entered the trial. It is the responsibility of the investigator at site to ensure that the follow-up data required by the protocol are collected and reported.

After the study has completed and final results are available, investigators may share these at the request of individual patients.

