2. STUDY OBJECTIVES AND ENDPOINTS

Objectives

Primary Objectives

- To select an optimal dose of DTP3 for further clinical evaluation [Recommended Phase 2 Dose (RP2D)] in patients with relapsed or refractory multiple myeloma or diffuse large B-cell lymphoma
- To assess the preliminary clinical efficacy of DTP3 in patients with relapsed or refractory multiple myeloma or diffuse large b-cell lymphoma

Secondary Objectives

- To assess the Dose Limiting Toxicity (DLT) and Maximum Tolerated Dose (MTD) of DTP3
- To assess the safety and tolerability of DTP3 in patients with relapsed or refractory multiple myeloma or diffuse large B-cell lymphoma
- To assess the pharmacokinetics of DTP3 in patients with relapsed or refractory multiple myeloma or diffuse large B-cell lymphoma
- To assess the pharmacodynamic activity of DTP3 in patients with relapsed or refractory multiple myeloma or diffuse large B-cell lymphoma
- To correlate GADD45β expression with pharmacodynamic and clinical response in patients with relapsed or refractory multiple myeloma or diffuse large B-cell lymphoma

Endpoints

Primary Endpoints

- Incidence, nature, and severity of all AEs, SAEs and DLTs
- Overall Response Rate (ORR)
 - **MM**: best overall response of stringent complete response (sCR), complete response CR, very good partial response (VGPR) or partial response (PR)
 - **DLBCL**: best overall response of PR or CR

Secondary Endpoints

- Changes in laboratory parameters, ECGs, vital signs
- Extent of exposure to DTP3
- PK parameters
- PD biomarkers of pathway-specific response:
- Correlation of GADD45¹ expression with pharmacodynamic and clinical response
- Relative reduction in levels of M protein and free light chains [MM only]
- Clinical Benefit Rate
 - MM: minimal response (MR) or better
 - **DLBCL**: CR plus PR plus stable disease (SD)

- Time to Response TTR)
- Duration of Response (DOR)
- Progression Free Survival (PFS)
- Event Free Survival [time to death, disease progression or initiation of non-protocol anti-cancer therapy] (EFS)
- Overall Survival (OS)

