	points idealy within +/- 2 minutes. For samples taken after the first hour, there can be a
	small window of +/- 5 minutes, for samples taken at 12 hours and later a window of 30
	minutes is allowed. The exact time of bleeding will anyway be registered on the log.
b	Pre infusion, 0.5hr, 1hr,2hr and 4hr (post-infusion)
	These samples will be collected 24 hours (range 18-36 hours) after completion of
	administration of the FOURTH dose of DTP3.
c	Further samples will be collected if a complete response is suspected or clinically required
	as determined by the Investigator
d	Patients receiving DTP3 after cycle 3 will continue with the assessments scheduled as per
-	cycle 3
	Dose Escalation Stage:
	Week 1 and 2: During Cycle 1, BP, pulse rate and 12 lead ECG will be carried out 15 min
	before and 30 mins, 60 min and 120 min after end of each DTP3 infusion (+/- 5mins).
	Week 3 and 4. During Cycle 1, BP, pulse rate and 12 lead ECG will be carried out 15 min before and 30 mins after end of each DTP3 infusion (+/- 5mins).
	Cycle 2-onwards : BP, pulse rate and 12 lead ECG will be carried out 15 min before and 30
	mins after end of each DTP3 infusion (+/- 5mins).
e	Cohort Expansion Stage:
	Week 1: During Cycle 1, BP, pulse rate and 12 lead ECG will be carried out 15 min before
	and 30 mins, after end of each DTP3 infusion.
	Week 2 onwards : BP, pulse rate and 12 lead ECG will be carried out before the first dose
	of DTP3 at the beginning of week 2 onwards (eg. before dose 4,7,10 etc)
f	Only to be done on a monthly basis in patients with detectable urinary M protein at
	screening
g	Pre-infusion
h	Bone marrow aspirate and biopsy required if radiological complete response
-	Serum pregnancy test (where appropriate) at beginning of each cycle of DTP3 and then
i	monthly for six months after cessation of DTP3 therapy.
j	To continue 8 weekly for evaluation as long as participating
	Where this is no Disease Progression when ceasing DTP3 treatment, survival status to
	continue being recorded for a period of six months after the last patient has been
k	recruited into the study. Via clinic team if under their care, or six weekly via family
	member.
1	Possible tests pending patient outcome of disease progression or complete resolution and
	local institutional practice:
	If at any point, a complete reponse is suspected in a patient, they will undergo:
	MM:
	 Two independent measurements (according to normal institutional practice)
	confirming:
	-negative immunofixation serum

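### EFS counts the start of non-protocol anti-cancer therapy as an event, but section 7.7 asks for later therapy only in patients who have already progressed, so EFS as collected largely reduces to PFS.

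*Protocol*

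**What the plan says.** The endpoint list in Protocol section 2 defines "Event Free Survival [time to death, disease progression or initiation of non-protocol anti-cancer therapy] (EFS"). Section 8.3 plans a Kaplan-Meier analysis of EFS alongside PFS, DOR and overall survival.

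Section 7.7 divides follow-up by status when DTP3 stops:

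- Without progression: patients "will be followed, through routinely scheduled clinic visits for disease progression [according to the schedule in 7.5 above] and survival", until six months after the last patient is recruited.
- With progression: these patients are "followed up through routinely scheduled clinic visits for subsequent anti-cancer therapies and survival".

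The sentence in 7.7 that sets the minimum frequency of follow-up again names only progression and survival status. The end-of-treatment page of Appendix C has a line for survival status and none for subsequent therapy. Its footnote k begins "Where this is no Disease Progression when ceasing DTP3 treatment, survival status to" and goes on to survival recording only.

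Section 7.6 deals with a new regimen as a safety matter. The visit must come before the next regimen, "any new drug treatments should start after the minimum 5 days washout period from DTP3", and if the new regimen is due within 28 days "this call can take place immediately before the patient is to commence a new treatment regime". The call is there to capture adverse events.

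**The concern.** New therapy affects EFS only when it comes before progression and death. Section 7.7 asks for it where it cannot change EFS and leaves it out where it can. The omitted group is foreseen: section 4.3.1 lists toxicity, clinical reasons unrelated to DTP3, symptomatic deterioration and withdrawal of consent to treatment among the reasons for stopping, and wants these patients kept in follow-up.

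Three things are at stake:

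- **EFS.** It would be reported as a separate endpoint while carrying little information beyond PFS.
- **PFS and DOR.** Time spent on the next drug cannot be separated from time attributable to DTP3, because the date needed for censoring is not asked for.
- **ORR, as a secondary risk.** Section 7.7 keeps patients without progression on the section 7.5 response schedule. Section 11.3 allows alternative treatment and keeps participants in follow-up and analysis. Section 2 defines ORR by best overall response with no stated end to the assessment period.

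**Working it through.** **1. When EFS and PFS differ.** Let D, P and N be the times of death, progression and start of non-protocol therapy.

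- PFS = min(D, P)
- EFS = min(D, P, N)

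The two differ only in a patient with N < min(D, P).

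**2. Set this against what section 7.7 collects.**

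- *Progressed when DTP3 stops.* P falls at or before the stop. Section 7.6 places a new drug after the stop, so N > P and EFS = P whatever N is. N is collected.
- *Not progressed when DTP3 stops.* N can precede P and D, so N can decide EFS. N is not listed.

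If N is unrecorded in the second group, the recorded EFS is min(D, P), which is PFS.

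**3. Look for N elsewhere in the Protocol.**

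- *7.6, visit.* Concomitant medications are taken at a visit that must precede the next regimen, so N has not yet occurred.
- *7.6, call.* A call moved forward to just before a new regimen leaves a trace of a start within 28 days of the last dose. No start-date item is specified.
- *After day 28.* No section asks for N in these patients.
- *4.3.2.* Off-study assessments before alternative therapy apply to withdrawal from the study, which 4.3.1 separates from stopping treatment.
- *Appendix C.* It has no line for subsequent therapy. It omits the item for progressed patients too, although 7.7 requires it there, so this silence is weak evidence taken alone.

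**4. How sensitive the ORR criterion is to one response.** The exact one-sided 90% lower limit is the 0.10 quantile of Beta(x, n − x + 1).

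- x = 10, n = 24: Beta(10, 15) gives 27.7%. This reproduces the figure in section 8.1.
- x = 9, n = 24: Beta(9, 16) gives 24.1%.

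The 25% minimum in section 8.1 lies between the two, so one response can decide a cohort of 24.

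**5. Illustration for ORR, with assumed inputs.** Take a true DTP3 ORR of 25%, n = 24 and no response cut-off. Let q be the share of DTP3 non-responders who stop without progression, start another drug and stay under assessment. Let r be the response rate on that drug. Apparent ORR = 0.25 + 0.75·q·r. With q = 0, P(10 or more of 24) = 5.5%.

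| q | r = 1/3: apparent ORR | P(≥10) | r = 1/2: apparent ORR | P(≥10) |
|---|---|---|---|---|
| 5% | 26.3% | 7.3% | 26.9% | 8.4% |
| 10% | 27.5% | 9.6% | 28.8% | 12.2% |
| 20% | 30.0% | 15.3% | 32.5% | 22.6% |

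Section 1.1 says that about a third of such myeloma patients respond usefully to available strategies, which is the basis for r = 1/3. The documents give no value for q, so the table shows sensitivity and is not a forecast.

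**The case against.** The strongest reply is that this is a wording gap affecting one component of a secondary, descriptive endpoint. Much of that reply stands.

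- A reader might infer that EFS cannot be measured at all. It can in part: death and progression are still recorded, and starts within 28 days may be traceable through 7.6.
- A reader might want to state how far EFS would be overstated. The documents give no rate of switching without progression. A calculation that assumes immediate switching would also concern the very starts that 7.6 may reveal. Eligibility points to few prompt switches: DLBCL patients must have no standard regimen available, and neither cohort may include current transplant or CAR T-cell candidates.
- A reader might infer that ORR is already contaminated and beyond repair in a SAP. It is not shown to be. A SAP could end response assessment at the End of Treatment Visit, which must precede the next regimen, without knowing when the new therapy started. A rule of that kind is commonly left to the SAP, and the SAP is not at hand.
- The comparison of 9 with 10 out of 24 needs care. The planned 24 are response-evaluable patients. Someone who stops at week 6 without progression is not one of them and may be replaced, while the efficacy set in section 8.2 is all dosed patients, so its denominator may exceed 24. The comparison fits better a patient assessed after two cycles who then stops without progression and switches.

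It can also be said that the EFS definition itself implies collection of the date, and that the eCRF, which is not shown, may hold it. But 7.7 is where the Protocol tells sites what to follow, and it names subsequent therapy for one group only.

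**Conclusion.** The mismatch between the EFS definition in section 2 and the collection rule in section 7.7 stands. Followed as written, the component that separates EFS from PFS goes largely uncollected in the only patients in whom it matters. The gap is complete for starts after day 28 and partial before then. A SAP can set a censoring rule for PFS and DOR, but it cannot apply one at new therapy without a date that sites are not asked to record.

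The ORR exposure is a secondary risk that a SAP could limit. It is not a demonstrated error, and its frequency is unknown from the documents. The conclusion assumes that the eCRF follows section 7.7. The point should be fixed, but it does not undermine the design.

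**What to change.** In section 7.7, require the start date and type of any subsequent anti-cancer therapy in **all** patients who stop DTP3, whether or not they have progressed. Add the item beside survival status in the Appendix C schedule, and to the eCRF.

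Preferably also state in section 8.3 that best overall response uses only assessments made before the start of non-protocol anti-cancer therapy.

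The cost is one extra data item at clinic and survival contacts that already take place, plus one clause in the ORR definition. EFS may come out slightly shorter and ORR slightly lower. The change is best made prospectively, since start dates missed during follow-up may be hard to recover. Dosing and clinical management are not affected.
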